9.1.4.5. Diabetes Education and Nutritional Counseling

Initial training at Visit 2 will include diabetes education and nutritional counseling including information on hypoglycemia recognition and management. Appropriate site personnel will administer training and education using locally approved diabetes education/training materials and programs or by using other materials that may be provided by the sponsor. Patients may be provided abbreviated training and education at visits following Visit 2 based upon patient needs.

9.2. Adverse Events

Investigators are responsible for monitoring the safety of patients who have entered this study and for alerting Lilly or its designee to any event that seems unusual, even if this event may be considered an unanticipated benefit to the patient.

The investigator is responsible for the appropriate medical care of patients during the study.

Investigators must document their review of each laboratory safety report.

The investigator remains responsible for following, through an appropriate health care option, AEs that are serious or otherwise medically important, considered related to the IP or the study, or that caused the patient to discontinue the IP before completing the study. The patient should be followed until the event resolves, stabilizes with appropriate diagnostic evaluation, or is reasonably explained. The frequency of follow-up evaluations of the AE is left to the discretion of the investigator.

Lack of drug effect is not an AE in clinical studies, because the purpose of the clinical study is to establish treatment effect.

After the informed consent form (ICF) is signed, study site personnel will record via electronic data entry the occurrence and nature of each patient's preexisting conditions, including clinically significant signs and symptoms of the disease under treatment in the study. In addition, site personnel will record any change in the condition(s) and any new conditions as AEs.

Investigators should record their assessment of the potential relatedness of each AE to protocol procedure and/or IP, via electronic data entry.

The investigator will interpret and document whether or not an AE has a reasonable possibility of being related to study treatment, study device, or a study procedure, taking into account the disease, concomitant treatment, or pathologies.

A "reasonable possibility" means that there is a cause and effect relationship between the IP, study device, and/or study procedure and the AE.

The investigator answers yes/no when making this assessment.

Planned surgeries and nonsurgical interventions should not be reported as AEs unless the underlying medical condition has worsened during the course of the study.

If a patient's IP is discontinued as a result of an AE, study site personnel must report this to Lilly or its designee via electronic data entry, clarifying if possible the circumstances leading to any dosage modifications or discontinuations of treatment.

9.2.1. *Serious Adverse Events*

An SAE is any AE from this study that results in one of the following outcomes:

- Death
- Initial or prolonged inpatient hospitalization
- A life-threatening experience (that is, immediate risk of dying)
- Persistent or significant disability/incapacity
- Congenital anomaly/birth defect
- Considered significant by the investigator for any other reason: important medical events that may not result in death, be life-threatening, or require hospitalization may be considered serious, based upon appropriate medical judgment.
- When a condition related to the prefilled pen necessitates medical or surgical intervention to preclude either permanent impairment of a body function or permanent damage to a body structure, the serious outcome of "required intervention" will be assigned.
- Severe hypoglycemia events: episodes of severe hypoglycemia as determined by the investigator according to the definition provided in Sections 9.4.1 and 9.4.2 must be reported as SAEs

Although all AEs occurring after signing the ICF are recorded in the case report form (CRF), SAE reporting begins after the patient has signed the ICF and has received IP. However, if an SAE occurs after signing the ICF, but prior to receiving IP, it needs to be reported ONLY if it is considered reasonably possibly related to study procedure.

Study site personnel must alert Lilly or its designee of any SAE within 24 hours of investigator awareness of the event via a sponsor-approved method. If alerts are issued via telephone, they are to be immediately followed with official notification on study-specific SAE forms. This 24-hour notification requirement refers to the initial SAE information and all follow-up SAE information.

Pregnancy (during maternal or paternal exposure to IP) does not meet the definition of an AE. However, to fulfill regulatory requirements any pregnancy should be reported following the SAE process to collect data on the outcome for both mother and fetus.

Investigators are not obligated to actively seek AEs or SAEs in patients once they have discontinued and/or completed the study (the patient summary CRF has been completed). However, if the investigator learns of any SAE, including a death, at any time after a patient has

been discharged from the study, and the investigator considers the event reasonably possibly related to the study treatment or study participation, he/she must promptly notify Lilly.

9.2.1.1. Suspected Unexpected Serious Adverse Reactions

Suspected unexpected serious adverse reactions (SUSARs) are serious events that are not listed in the IB and that the investigator identifies as related to IP or procedure. United States 21 CFR 312.32 and European Union Clinical Trial Directive 2001/20/EC and the associated detailed guidances or national regulatory requirements in participating countries require the reporting of SUSARs. Lilly has procedures that will be followed for the recording and expedited reporting of SUSARs that are consistent with global regulations and the associated detailed guidances.

9.2.2. Complaint Handling

Lilly collects product complaints on IP and drug delivery systems used in clinical studies in order to ensure the safety of study participants, monitor quality, and to facilitate process and product improvements.

Patients will be instructed to contact the investigator as soon as possible if he or she has a complaint or problem with the IP and/or drug delivery system so that the situation can be assessed.

- Complaints must be reported by site staff within 24 hours of notification to the clinical site/study personnel, or within 24 hours of study/site personnel becoming aware of a product issue, regardless of the availability of the complaint sample.
- Retain the IP under appropriate storage conditions, if available or when obtained, until instructed to return it to Lilly.
- Product complaints for non-Lilly Products (including concomitant drugs) that do not have a Lilly Product Batch or Control number, are reported directly to the manufacturer per product label.
- Follow the instructions outlined in the Product Complaint Form for other reporting requirements.

9.3. Treatment of Overdose

Excess insulin administration may result in hypoglycemia. Refer to the IB for LY900014 and product label for insulin lispro.

9.4. Safety

9.4.1. Hypoglycemia

Patients are encouraged to perform SMBG whenever hypoglycemia may be suspected, either by symptoms experienced or perceived increased risk as related to dietary intake, physical activity, or inadvertent or atypical insulin dosing. All patients will be instructed to treat a BG ≤ 70 mg/dL (3.9 mmol/L) as hypoglycemia.

Hypoglycemia events will be collected in eCOA (Section 9.1.4.1). If a hypoglycemia event is suspected, the patient should record the BG value, any associated symptoms, and the treatment administered in eCOA. The patient should contact the site as necessary. Reports of hypoglycemia will be classified by the investigator as “severe” or “not severe” based upon data collected in eCOA and in consultation with the patient, see below and Section 9.2.1. All episodes of severe hypoglycemia must be reported as AEs via electronic data entry, and as SAEs.

Hypoglycemia will be described using the following definitions:

- **Documented hypoglycemia**
 - **Documented symptomatic hypoglycemia:** an event during which typical symptoms of hypoglycemia are accompanied by BG of ≤ 70 mg/dL (3.9 mmol/L);
 - **Documented asymptomatic hypoglycemia:** an event not accompanied by typical symptoms of hypoglycemia but with a BG concentration of ≤ 70 mg/dL (3.9 mmol/L);
 - **Documented unspecified hypoglycemia:** an event during which BG ≤ 70 mg/dL (3.9 mmol/L) but no information relative to symptoms of hypoglycemia were recorded;
- **Probable symptomatic hypoglycemia:** an event during which symptoms are indicative of hypoglycemia and which was presumably caused by BG ≤ 70 mg/dL (3.9 mmol/L) although no BG measurement was reported;
- **Severe hypoglycemia:** An event requiring assistance of another person to actively administer carbohydrate, glucagon, or other resuscitative actions. During these episodes, the patient has an altered mental status and cannot assist in his/her own care, may be semiconscious or unconscious, or experience coma with or without seizures, and may require parenteral therapy. BG measurements may not be available during such an event, but neurological recovery attributable to the restoration of BG concentration to normal is considered sufficient evidence that the event was induced by a low BG concentration (BG ≤ 70 mg/dL [3.9 mmol/L]).
- **Nocturnal hypoglycemia:** any hypoglycemic event (documented hypoglycemia or probable symptomatic hypoglycemia, including severe hypoglycemia) that occurs between bedtime and waking.
- **Relative hypoglycemia:** an event during which typical symptoms of hypoglycemia, that do not require the assistance of another person, are accompanied by BG > 70 mg/dL (3.9 mmol/L), but these levels may be quickly approaching the 70 mg/dL (3.9 mmol/L) threshold.
- **Overall hypoglycemia:** This category combines all cases of hypoglycemia (documented hypoglycemia and probable symptomatic hypoglycemia, including severe hypoglycemia) excluding the events of relative hypoglycemia. If an event of hypoglycemia falls into multiple subcategories, the event is only counted once in this category.

9.4.2. Severe Hypoglycemia

The determination of a hypoglycemic event as an episode of severe hypoglycemia, as defined above, is made by the investigator based upon the medical need of the patient to have required assistance and is not predicated on the report of a patient simply having received assistance.

9.4.3. Electrocardiograms

For each patient, ECGs should be performed at Visit 1 according to the study specific requirements described in the Schedule of Activities (Section 2).

ECGs will be interpreted by a qualified physician (the investigator or qualified designee) at the site as soon after the time of ECG collection as possible, and ideally while the patient is still present, to determine whether the patient meets entry criteria and for immediate patient management, should any clinically relevant findings be identified.

ECGs may be obtained at additional times, when deemed clinically necessary.

9.4.4. Vital Signs

For each patient, vital signs measurements should be conducted according to the Schedule of Activities (Section 2) including the study specific requirements.

9.4.5. Laboratory Tests

For each patient, laboratory tests detailed in [Appendix 2](#) should be conducted according to the Schedule of Activities (Section 2).

Any clinically significant findings from laboratory tests that result in a diagnosis and that occur after the patient receives the first dose of IP should be reported to Lilly or its designee as an AE via electronic data entry.

9.4.6. Safety Monitoring

Lilly will periodically review evolving aggregate safety data within the study by appropriate methods.

If a study patient experiences elevated ALT ≥ 3 X ULN, ALP ≥ 2 X ULN, or elevated TBL ≥ 2 X ULN, clinical and laboratory monitoring should be initiated by the investigator. Details for hepatic monitoring depend upon the severity and persistence of observed laboratory test abnormalities. To ensure patient safety and comply with regulatory guidance, the investigator is to consult with the Lilly CRP regarding collection of specific recommended clinical information and follow-up laboratory tests. See [Appendix 4](#).

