6.2. Exclusion Criteria

Patients will be excluded from study enrollment if they meet any of the following criteria at screening:

Medical Conditions

- [15] Having any other condition (including known drug or alcohol abuse, psychiatric disorder including eating disorder) that precludes the patient from following and completing the protocol
- [16] Have been diagnosed, at any time, with T1D or Latent Autoimmune Diabetes in Adults
- [17] Have hypoglycemia unawareness as judged by the investigator
- [18] Have had any episode of severe hypoglycemia (defined as requiring assistance due to neurologically disabling hypoglycemia) within the 6 months prior to screening
- [19] Have had 1 or more episodes of diabetic ketoacidosis or hyperglycemic hyperosmolar state within the 6 months prior to screening
- [20] Have a known diagnosis of secondary diabetes (for example, diabetes caused by hemochromatosis, acromegaly, chronic pancreatitis, or pancreatectomy)
- [21] Excessive insulin resistance defined as having received a total daily dose of insulin >2.0 U/kg at the time of screening
- [22] Have a history of or are being evaluated for bariatric surgery including Roux-en-Y gastric bypass surgery, gastric banding, and/or gastric sleeve
- [23] Have cardiovascular disease, within the last 6 months prior to screening, defined as stroke, decompensated heart failure New York Heart Association class III or IV ([Appendix 6](#)), myocardial infarction, unstable angina pectoris or coronary arterial bypass graft
- [24] Renal:
 - a) History of renal transplantation
 - b) Currently receiving renal dialysis
 - c) Serum creatinine >2.0 mg/dL (177 $\mu\text{mol/L}$) at screening
- [25] Hepatic: Have obvious clinical signs or symptoms of liver disease (for example, acute or chronic hepatitis or cirrhosis), or elevated liver enzyme measurements as indicated below at screening:
 - a) Total bilirubin level (TBL) $\geq 2X$ the upper limit of normal (ULN [with the exception of Gilberts Disease]) as defined by the central laboratory,

Or

b) Alanine aminotransferase (ALT) $\geq 3X$ ULN as defined by the central laboratory,

Or

c) Aspartate aminotransferase (AST) $\geq 3X$ ULN as defined by the central laboratory

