8.1. Discontinuation from Study Treatment

In the event that the patient is discontinued from the study treatment, the investigator should encourage the patient to remain in the study for continued safety monitoring.

Lilly recognizes the importance of complete data collection. This study includes elements to minimize missing data. Randomized patients who are discontinued from IP before study completion are encouraged to remain in the study for continued monitoring. For patients who remain in the study after early discontinuation of IP, both efficacy (including HbA1c) and safety data will be collected at scheduled visits. The difference between stopping IP and discontinuing the study will be explained to patients as part of the informed consent, and patients will be encouraged to continue in the study even if they stop study drug. In addition, study site investigators will be trained on the importance of complete data collection, with additional re-education of sites and patients as necessary.

8.1.1. *Permanent Discontinuation from Study Treatment*

Patients will be discontinued from the IP in the following circumstances:

- The investigator may decide that the patient should stop IP. If this decision is made because of an AE, SAE, or a clinically significant laboratory value, the study drug is discontinued for that patient and appropriate measures are to be taken. Lilly or its designee is to be alerted.
- The patient may decide to stop IP.
- If the patient becomes pregnant.
- If an investigator, study site personnel performing assessments, or patient is unblinded, the patient must discontinue IP.
- If the patient, for any reason, requires treatment with another therapeutic regimen or therapeutic agent that has been demonstrated to be effective for treatment of the study indication. Discontinuation from IP should occur prior to introduction of the new agent.
- Use of prohibited concomitant medication, see [Table ITRN.8](#).
- If the patient has not taken IP for more than 14 consecutive days.

Discontinuation of the IP for abnormal liver tests **should be considered** by the investigator when a patient meets one of the following conditions after consultation with the Lilly designated medical monitor:

- ALT or AST >8X ULN.
- ALT or AST >5X ULN for more than 2 weeks.
- ALT or AST >3X ULN and TBL >2X ULN or prothrombin time >1.5X ULN.

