- ALT or AST >3X ULN with the appearance of fatigue, nausea, vomiting, right upper-quadrant pain or tenderness, fever, rash, and/or eosinophilia (>5%).
- alkaline phosphatase (ALP) >3X ULN.
- ALP >2.5X ULN and TBL >2X ULN.
- ALP >2.5X ULN with the appearance of fatigue, nausea, vomiting, right upper-quadrant pain or tenderness, fever, rash, and/or eosinophilia (>5%).

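### Protocol 9.4.6 omits AST from the values that start directed hepatic monitoring and sponsor consultation, leaving an isolated AST rise of 3X to 8X ULN to investigator judgment

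*Protocol*

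**What the plan says.** **Monitoring (Protocol 9.4.6).** Three findings act as triggers: ALT ≥3X ULN, ALP ≥2X ULN and TBL ≥2X ULN. On any of them, "clinical and laboratory monitoring should be initiated by the investigator", and "the investigator is to consult with the Lilly CRP regarding collection of specific recommended clinical information and follow-up laboratory tests". AST is not named.

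**Stopping (Protocol 8.1.1).** The investigator should consider stopping investigational product (IP) for abnormal liver tests "when a patient meets one of the following conditions after consultation with the Lilly designated medical monitor". Four of the listed conditions name AST with ALT:

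- A high value that counts by itself: "ALT or AST >8X ULN".
- A lower value that has to persist: "ALT or AST >5X ULN for more than 2 weeks".
- A moderate value joined to a second abnormal test, either bilirubin or clotting: "ALT or AST >3X ULN and TBL >2X ULN or prothrombin time >1.5X ULN".
- A moderate value joined to clinical signs or a raised eosinophil count. The wording begins "ALT or AST >3X ULN with the appearance of fatigue, nausea, vomiting" and the list then goes on to other signs.

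**Entry (Protocol 6.2, criterion 25).** Patients are excluded for "elevated liver enzyme measurements as indicated below at screening". The limits that follow are ≥3X ULN for ALT and, separately, ≥3X ULN for AST.

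**Reporting (SAP 6.12.4.4.3).** AST is tabulated at the same multiples as ALT. Individual profiles and a listing are produced for patients with ALT or AST ≥3X ULN, or TBL ≥2X ULN.

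**Testing (Protocol Appendices 2 and 4).** AST is in the routine chemistry panel. Appendix 4 permits selected tests after a treatment-emergent hepatic abnormality, and allows that they may be required in consultation with the sponsor's physician. Its list includes AST and prothrombin time, but it sets no enzyme threshold.

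**The concern.** For ALT, ALP and TBL, the 9.4.6 trigger lies at or below the level that counts in 8.1.1. Monitoring and consultation are thus prompted before, or as, stopping has to be considered. AST has stopping conditions but no monitoring trigger, and neither document gives a reason for treating it differently at this one step.

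What is at stake is the handling of individual patients. Two of the 8.1.1 conditions need information that a single routine AST result does not supply: persistence beyond two weeks needs a repeat AST, and the prothrombin-time alternative needs a test outside the routine panel. For ALT, the instruction in 9.4.6 to monitor and to agree follow-up tests leads towards that information. For an isolated AST rise no equivalent instruction applies, so whether the information is sought depends on the investigator.

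**Working it through.** No sample size, alpha or event count enters this point, so the check sets the rules side by side.

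**Step 1. Compare trigger levels (multiples of ULN).**

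| Test | 9.4.6 trigger | Levels used in 8.1.1 |
|---|---|---|
| ALT | ≥3X | >3X with another feature; >5X for more than 2 weeks; >8X |
| AST | none | same as ALT |
| ALP | ≥2X | >2.5X with another feature; >3X |
| TBL | ≥2X | >2X, in combination |

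AST is the only one of the four without a 9.4.6 trigger.

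**Step 2. Trace an isolated AST rise** (ALT <3X, ALP <2X and TBL <2X ULN).

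| AST level | 9.4.6 | 8.1.1 consultation |
|---|---|---|
| exactly 3X | not triggered | not met |
| >3X to 5X | not triggered | only with prothrombin time >1.5X ULN, or listed symptoms or eosinophilia |
| >5X to 8X | not triggered | as above, or if it lasts more than 2 weeks |
| >8X | not triggered | met on the AST value alone |

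The band with no threshold-based instruction to consult is therefore 3X to 8X ULN, unless another 8.1.1 feature is already known. Above 8X, 8.1.1 supplies the consultation although 9.4.6 is still silent.

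**Step 3. Ask where the data for the four AST conditions come from.**

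- >8X: one chemistry result.
- >3X with symptoms or eosinophilia: AE recording and the routine hematology panel, which includes eosinophils.
- >3X with TBL or prothrombin time: the TBL part is covered, because TBL >2X itself triggers 9.4.6. Prothrombin time is absent from the Appendix 2 panel and appears only in Appendix 4.
- >5X for more than 2 weeks: needs a repeat AST.

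So one condition, and the prothrombin-time half of another, depend on follow-up testing that no AST threshold starts.

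**Step 4. Look for other text that would prompt follow-up.**

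- Appendix 1 counts an abnormal laboratory result as a possible AE.
- Protocol 9.2 requires documented review of each laboratory safety report and alerting the sponsor to anything unusual. AEs that are serious, medically important, related to IP or the study, or the cause of stopping IP must be followed until they resolve, stabilize after suitable evaluation or are explained. The frequency is left to the investigator.
- Protocol 9.4.5 requires AE reporting of significant laboratory findings that lead to a diagnosis.
- Protocol 8.1.1 has the sponsor alerted when IP is stopped for a significant laboratory value, which comes after the decision.
- Appendix 4 testing is permissive.

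These provisions allow follow-up, and 9.2 in practice implies repeating the AST. None directs monitoring or consultation at an AST threshold.

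**Step 5. Judge the reach.** SAP Table 6.2 places planned post-baseline chemistry at Visit 18 or the early discontinuation visit. By then IP is ending or already stopped (Protocol 7.2.1.5). What remains is unscheduled tests, follow-up of those end-of-treatment results, and possibly a Visit 8 result that returns after randomization. The last case is an assumption, since laboratory turnaround is not given. The documents do not allow a count of patients.

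**The case against.** The strongest opposing case has four parts.

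1. **General safeguards already cover the patient.** A reader might infer from the omission that nothing in the protocol prompts follow-up of an AST rise. The documents do not support that. An AST of 3X to 8X ULN can itself be an AE, and if it is judged medically important or related, 9.2 requires follow-up to resolution or stabilization, which means measuring it again. An investigator who has read 8.1.1 also knows that persistence above 5X matters. This part stands and limits the point. What it does not supply is a directed consultation at a stated AST level.
2. **The stopping decision is usually moot.** At Visit 18 or early discontinuation there is little or no IP left to stop. This stands, and is why the reach is called small.
3. **The lists differ by purpose.** ALP is in 9.4.6 and 8.1.1 but is neither an enzyme limit in criterion 25 nor a trigger for the SAP listing, so absence from one list does not prove an error. AST can also rise from causes outside the liver, a possible reason for leaving it out. It is fair that the documents do not show whether the omission was deliberate. But 8.1.1 already accepts AST for the weightier decision to stop IP, and a consultation is where a non-hepatic cause would be sorted out.
4. **The change mandates no repeat test or prothrombin time.** True, and 9.4.6 mandates neither for ALT. It would be wrong to infer that ALT has a fixed retest schedule that AST lacks. The difference is only the instruction to start monitoring and agree the tests with the sponsor's physician.

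**Conclusion.** The point holds in limited form. Section 9.4.6 gives no AST trigger, and an isolated AST rise of 3X to 8X ULN has no threshold-based instruction to monitor or consult unless another 8.1.1 feature is already known. Follow-up in that band rests on investigator judgment under the AE definition and 9.2, with optional Appendix 4 testing. The documents do not support saying that such patients go unfollowed, or that the 8.1.1 conditions could not be detected.

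The conclusion about the rules rests on the text alone. The reach rests on the chemistry schedule and, for Visit 8 results, on the turnaround assumption. It is a minor patient-safety wording point and a cheap improvement. The primary HbA1c analysis, the sample size and the type I error are untouched.

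**What to change.** In Protocol 9.4.6, insert *or AST* after ALT, so that the first trigger reads *elevated ALT or AST ≥3X ULN*. This brings AST under the existing monitoring, consultation and Appendix 4 pathway, and matches criterion 25 and the SAP listing threshold. Repeat timing and prothrombin time would still be settled in the consultation, as they are for ALT.

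The cost is one phrase in the protocol, with no new scheduled visit or routine test. The downside is a few extra unscheduled tests, some for AST rises that are not of liver origin.
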